7.1 Adverse events

An adverse event (AE) is any untoward medical occurrence (e.g., any unfavorable and unintended sign [including abnormal laboratory findings], symptom or disease) in a patient or clinical investigation patient from randomization (Visit 101) until the end of study visit (16 weeks after the last IMP injection). Any events occurring during the Screening and Baseline Epochs and conditions that were already present at the time of informed consent should be documented as medical history. An AE may or may not be temporally or causally associated with the use of a medicinal (investigational) product.

In addition, all reports of intentional misuse and abuse of the product are also considered an adverse event irrespective if a clinical event has occurred.

The occurrence of adverse events must be sought by non-directive questioning of the patient at each visit during the study. Adverse events also may be detected when they are volunteered by the patient during or between visits or through physical examination findings, laboratory test findings, or other assessments.

Abnormal laboratory values or test results constitute adverse events only if they fulfill at least one of the following criteria:

- they induce clinical signs or symptoms,
- they are considered clinically significant,
- they require therapy.

Clinically significant abnormal laboratory values or test results must be identified through a review of values outside of normal ranges/clinically notable ranges, significant changes from baseline or the previous visit, or values which are considered to be non-typical in patient with underlying disease. Investigators have the responsibility for managing the safety of individual patient and identifying adverse events. Alert ranges for laboratory and other test abnormalities are included in Appendix 1.

Adverse events must be recorded in the Adverse Events eCRF under the signs, symptoms or diagnosis associated with them, accompanied by the following information:

- the severity grade
 - mild: usually transient in nature and generally not interfering with normal activities
 - moderate: sufficiently discomforting to interfere with normal activities
 - severe: prevents normal activities
- its relationship to the study treatment
 - Yes
 - No

- its duration (start and end dates) or if the event is ongoing an outcome of not recovered/not resolved must be reported.

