7.3 Liver safety monitoring

To ensure patient safety and enhance reliability in determining the hepatotoxic potential of an investigational drug, a standardized process for identification, monitoring and evaluation of liver events has to be followed.

The following two categories of abnormalities/adverse events have to be considered during the course of the study (irrespective of whether classified/reported as (S)AE):

- Liver laboratory triggers, which will require repeated assessments of the abnormal laboratory parameter

- Liver events, which will require close observation, follow-up monitoring and completion of the standard base liver eCRF pages

Please refer to Table 13-1-Appendix 2 for complete definitions of liver laboratory triggers and liver events.

Every liver laboratory trigger or liver event as defined in Table 13-1-Appendix 2 should be followed up by the investigator or designated personnel at the trial site as summarized below. Detailed information is outlined in Table 13-2-Appendix 2.

For the liver laboratory trigger:

- Repeating the liver function test (LFT) within the next week to confirm elevation.

These LFT repeats must be performed using the central laboratory if possible. If this is not possible, then the repeats can be performed at a local laboratory to monitor the safety of the patient. Repeats laboratory must then be performed at central laboratory as soon as possible. If a liver event is subsequently reported, any local LFTs previously conducted that are associated with this event must be reported on the Liver eCRF pages.

- If the elevation is confirmed, close observation of the patient will be initiated, including consideration of treatment interruption if deemed appropriate.

For the liver events:

- Repeating the LFT to confirm elevation as appropriate
- Discontinuation of the investigational drug if appropriate
- Hospitalization of the patient if appropriate
- A causality assessment of the liver event via exclusion of alternative causes (e.g., disease, co-medications)
- An investigation of the liver event which needs to be followed until resolution.

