Appendix 1: Clinically notable laboratory values

Only selected lab parameters which have potential to be sensitive to erenumab exposure are listed.

Notable Values			
Laboratory Variable	Gender (M/F/Both)	Standard Units	SI Units
LIVER FUNCTION AND RELATED VARIABLES			
SGOT (AST)	F	>93 U/L	>93 U/L
SGOT (AST)	M	>111 U/L	>111 U/L
SGPT (ALT)	F	>90 U/L	>90 U/L
SGPT (ALT)	M	>123 U/L	>123 U/L
Total bilirubin	Both	>3.6 mg/dL	>63 µmol/L
Alkaline Phosphatase	F	>832 U/L	>832 U/L
Alkaline Phosphatase	M	>1032 U/L	>1032 U/L
HEMATOLOGY VARIABLES			
Neutrophils	Both	<1.5x 10 ³ /uL	<1.5x10 ⁹ /L

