> 5 to $\leq 8 \times \text{ULN}$	
 • Repeat LFT within 48 hours • If elevation persists, continue follow-up monitoring • If elevation persists for more than 2 weeks, discontinue the study drug • Establish causality 	ALT, AST, TBL, Alb, PT/INR, ALP and γ GT until resolution ^c (frequency at investigator discretion)

Criteria	Actions required	Follow-up monitoring
	
 Complete liver CRF 	
> 3 × ULN accompanied by symptoms ^b	
 Discontinue the study treatment immediately Hospitalize if clinically appropriate Establish causality Complete liver CRF 	ALT, AST, TBL, Alb, PT/INR, ALP and γGT until resolution ^c (frequency at investigator discretion)
> 3 to ≤ 5 × ULN (patient is asymptomatic)	
 Repeat LFT within the next week If elevation is confirmed, initiate close observation of the patient 	Investigator discretion Monitor LFT within 1 to 4 weeks
ALP (isolated)		
> 2 × ULN (in the absence of known bone pathology)	
 Repeat LFT within 48 hours If elevation persists, establish causality Complete liver CRF 	Investigator discretion Monitor LFT within 1 to 4 weeks or at next visit
TBL (isolated)		
> 2 × ULN (in the absence of known Gilbert syndrome)	
 Repeat LFT within 48 hours If elevation persists, discontinue the study drug immediately Hospitalize if clinically appropriate Establish causality Complete liver CRF 	ALT, AST, TBL, Alb, PT/INR, ALP and γGT until resolution ^c (frequency at investigator discretion) Test for hemolysis (e.g., reticulocytes, haptoglobin, unconjugated [indirect] bilirubin)
> 1.5 to ≤ 2 × ULN (patient is asymptomatic)	
 Repeat LFT within the next week If elevation is confirmed, initiate close observation of the patient 	Investigator discretion Monitor LFT within 1 to 4 weeks or at next visit
Jaundice	
 Discontinue the study treatment immediately Hospitalize the patient Establish causality Complete liver CRF 	ALT, AST, TBL, Alb, PT/INR, ALP and γGT until resolution ^c (frequency at investigator discretion)
Any AE potentially indicative of a liver toxicity*	
 Consider study treatment interruption or discontinuation Hospitalization if clinically appropriate Establish causality Complete liver CRF 	Investigator discretion

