### **2.8.1 Adverse events (AEs)**

In the frame of safety analysis the following treatment-emergent AE types will be considered:

- Any AE
- Study treatment related AE
- AE leading to study treatment discontinuation
- AE leading to dose adjustment (including study treatment discontinuation)
- AE leading to pausing in uptitration

- Serious AE (SAE)
- Study treatment related SAE
- SAE leading to study treatment discontinuation
- Death

All adverse events tables will be summarized by treatment group.

The Medical Dictionary for Regulatory Activities (MedDRA) version 22.1 or later will be used to code all adverse events (AE) to a system organ class (SOC) and a preferred term (PT).

Overview table of the number and percentage of patients having each type of AE.

Tables with the *summary types I* will be provided for all AEs listed above except for death. Tables with the *summary types II* will only be provided for AE type ‘any AE’.

*Summary type I:* Tables with number and percentage of patients having particular AE summarized by treatment group, SOC and PT. Summaries will be provided for each AE type separately.

*Summary type II:* Tables with number and percentage of patients having particular AE summarized by treatment group, SOC, PT and severity. Summaries will be provided for each AE type separately.

The SOCs will be presented in the alphabetic order and PTs will be ordered within the SOCs by decreasing order of frequency in the erenumab treatment group.

If a patient reported more than one adverse event with the same PT, the adverse event with the greatest severity will be presented. If a patient reported more than one adverse event within the same primary system organ class, the patient will be counted only once with the greatest severity at the system organ class level, where applicable.

All AEs, deaths (see [Section 2.8.2](#) for details), SAEs and AEs leading to permanent study drug discontinuation will be listed separately.

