### **2.8.3 Laboratory data**

Summary statistics of laboratory hematology- and blood chemistry results will be presented as absolute value as well as change from baseline by visit, treatment and laboratory test category. Change from baseline will be summarized for each time point and only for patients with both baseline and post-baseline assessment.

Clinically notable laboratory values will be flagged and listed by treatment group.

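### The SAP flags ALP and bilirubin by cut-offs that exceed the protocol's liver-event limits whenever the ULN is below 416/516 U/L (ALP, F/M) or 1.8 mg/dL (bilirubin), leaving the by-arm liver summary incomplete

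*SAP*

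**What the plan says.** SAP 2.8.3 gives by-visit summary statistics for hematology and chemistry, then one rule for individual values: "Clinically notable laboratory values will be flagged and listed by treatment group". SAP Table 2.8.1.1-1 supplies the cut-offs and repeats protocol Appendix 1:

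- AST above 93 (F) / 111 (M) U/L
- ALT above 90 (F) / 123 (M) U/L
- total bilirubin above 3.6 mg/dL, also given as 63 µmol/L
- ALP above 832 (F) / 1032 (M) U/L

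Appendix 1 describes its scope in these words: "Only selected lab parameters which have potential to be sensitive to erenumab exposure are listed". Protocol 6.5.4 makes it the definition of clinically notable findings, and protocol 7.1 adds: "Alert ranges for laboratory and other test abnormalities are included in Appendix 1".

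Protocol Appendix 2 works in multiples of the ULN. Table 13-1 sets liver triggers at ALT/AST above 3× up to 5×ULN and bilirubin above 1.5× up to 2×ULN. It sets liver events at ALT or AST above 5×ULN, ALP above 2×ULN without known bone pathology, and bilirubin above 2×ULN without known Gilbert syndrome. A potential Hy's Law case is ALT or AST above 3×ULN with bilirubin above 2×ULN and no ALP rise beyond 2×ULN.

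Protocol 7.3 provides for "Liver events, which will require close observation, follow-up monitoring and completion of the standard base liver eCRF pages", and says that this applies "irrespective of whether classified/reported as (S)AE".

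**The concern.** The plan holds two liver yardsticks. One decides who has a liver event, and the other decides whose laboratory values the report flags. If the second is laxer, patients who meet the protocol's own definition drop out of the laboratory listing.

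Other outputs do not clearly fill the gap. Liver events need not be recorded as adverse events, so the AE listing may not hold them all. SAP 2.8.1.1 marks AEs of special interest as not applicable. By-visit statistics give no patient counts and cannot show ALT/AST, bilirubin and ALP together in one patient, which the Hy's Law definition needs. Protocol 9.5.1.2 also plans maximum change from baseline within each study period, and SAP 2.8.3 does not carry this over.

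The trial compares the tolerability and safety of two drugs and is meant to support health technology assessment. The protocol collects liver events on dedicated eCRF pages, yet the readable SAP never reports them by arm.

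**Working it through.** **Inputs.** The cut-offs are from SAP Table 2.8.1.1-1 and protocol Appendix 1, and the liver-event limits from protocol Table 13-1. No ULN is given in either document. The assumed ranges are ALP 100–150 U/L and bilirubin 1.0–1.3 mg/dL, with higher stress values. The cut-offs cannot be reproduced from the documents, which do not say what multiple of the ULN they represent.

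**Step 1: break-even ULN = cut-off / 2.** This is the ULN at which the listing rule and the liver-event limit coincide.

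- ALP: 832/2 = 416 U/L (F); 1032/2 = 516 U/L (M)
- Bilirubin: 3.6/2 = 1.8 mg/dL

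Below these ULNs the listing cut-off is higher than the liver-event limit.

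**Step 2: size of the gap = cut-off / (2 × ULN).**

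| Analyte | Assumed ULN | 2×ULN | Cut-off / (2×ULN) |
|---|---|---|---|
| ALP, U/L | 100 | 200 | 4.16 (F), 5.16 (M) |
| ALP, U/L | 150 | 300 | 2.77 (F), 3.44 (M) |
| ALP, U/L (stress) | 300 | 600 | 1.39 (F), 1.72 (M) |
| Bilirubin, mg/dL | 1.0 | 2.0 | 1.80 |
| Bilirubin, mg/dL | 1.2 | 2.4 | 1.50 |
| Bilirubin, mg/dL | 1.3 | 2.6 | 1.38 |
| Bilirubin, mg/dL (stress) | 1.5 | 3.0 | 1.20 |

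Over the assumed ranges, the listing cut-off is about 2.8 to 5.2 times the liver-event limit for ALP and 1.4 to 1.8 times for bilirubin.

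**Step 3: which multiples the cut-offs may represent.** This is inferred from number patterns only.

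- ALP: 832 = 8 × 104 and 1032 = 8 × 129
- Bilirubin: 3.6 = 3 × 1.2 and 63 = 3 × 21
- AST: 93 = 3 × 31 and 111 = 3 × 37
- ALT: 90 = 3 × 30 and 123 = 3 × 41

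On that reading ALP is flagged at 8×ULN against a limit of 2×ULN (8/2 = 4-fold), and bilirubin at 3×ULN against 2×ULN (3/2 = 1.5-fold). The transaminases are flagged at 3×ULN, the lower edge of their trigger band and below their 5×ULN event limit.

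**Step 4: a potential Hy's Law patient.** On the Step 3 reading, ALT or AST above 3×ULN is flagged. With a bilirubin ULN of 1.2 mg/dL, bilirubin meets the Hy's Law condition above 2 × 1.2 = 2.4 mg/dL but is flagged only above 3.6 mg/dL. Between those values the patient has a transaminase flag and no bilirubin flag. The flags also cannot show whether ALP exceeds 2×ULN, because ALP is marked only above 832/1032 U/L.

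**Step 5: units.** With a conversion factor of 17.104, 3.6 mg/dL = 61.6 µmol/L. The stated 63 µmol/L is 63/61.57 − 1 = 2.3% higher, so the bilirubin rule differs slightly by unit.

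**The case against.** The strongest reply is that patient safety does not run through Appendix 1. Protocol 7.3 sends sites to Tables 13-1 and 13-2, which prescribe action at the ULN multiples. Protocol 7.1 also asks investigators to review values outside the normal range. A reader might infer that a site relying on the alert ranges would overlook a liver event; the documents do not support that.

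A reader might also infer that the comparative liver picture would be falsely clean. That too goes too far. All chemistry results enter the by-visit summaries. All AEs are listed, and "SAEs and AEs leading to permanent study drug discontinuation will be listed separately", so a liver event recorded as an AE appears there. What fails is narrower: no readable output guarantees that every patient meeting Table 13-1 is counted by arm.

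Other points on that side:

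- The size of the gap depends on ULNs that the documents do not give. This stands; the figures are conditional.
- A notable-value list and a liver-event algorithm may legitimately differ. That is so, but then something else has to report the liver events.
- Redacted text and the separate table shells might hold such an output. This cannot be excluded.
- Exclusion criterion 17 bars entry at bilirubin of 2×ULN or more. It is an entry rule and does not contradict a different on-treatment listing cut-off.
- The unit difference is 2.3% and may be rounding.
- Flags from laboratory values alone would miss Table 13-1's qualifiers on bone pathology and Gilbert syndrome. This stands and is built into the fix.

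**Conclusion.** The point holds as a reporting gap. SAP 2.8.3 would leave out of the laboratory listing those ALP and bilirubin values that lie above 2×ULN but not above the Appendix 1 cut-offs. The direction needs only a ULN below 416/516 U/L for ALP or 1.8 mg/dL for bilirubin. The size rests on the assumed ULNs: the gap is large for ALP and moderate for bilirubin, so calling both cut-offs far above the limit would overstate the bilirubin part.

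The consequence is an incomplete by-arm liver safety summary. Site detection, clinical follow-up, and the primary and secondary analyses are untouched. The change is worth making because it is cheap and reports the protocol's own definitions from data already collected.

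**What to change.** In SAP 2.8.3, add a by-arm n (%) table and a patient listing of the Table 13-1 laboratory criteria, using the central laboratory's ULNs:

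- ALT or AST above 3×ULN and above 5×ULN
- total bilirubin above 1.5×ULN and above 2×ULN
- ALP above 2×ULN
- concurrent ALT or AST above 3×ULN with bilirubin above 2×ULN and ALP not above 2×ULN, stating what counts as concurrent

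Mark patients with known bone pathology or Gilbert syndrome, as Table 13-1 does. Keep the Appendix 1 listing alongside.

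At the next protocol amendment, reconcile Appendix 1 with Appendix 2, say how the two are meant to relate, and align the two bilirubin units. Protocol 11.1 requires formal approval of an amendment, so this part is more than an editorial change, but the SAP fix does not depend on it.

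The cost of the SAP change is one extra descriptive table and one listing, with no new data collection and no new clinical threshold.

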**Table 2.8.1.1-1. Clinically notable laboratory values**

Notable values			
Laboratory variable	Gender (M/F/Both)	Standard Units	SI Units
Liver function and related variables			
SGOT (AST)	F	> 93 U/L	> 93 U/L
SGOT (AST)	M	> 111 U/L	> 111 U/L
SGPT (ALT)	F	> 90 U/L	> 90 U/L
SGPT (ALT)	M	> 123 U/L	> 123 U/L
Total bilirubin	Both	> 3.6 mg/dL	> 63 µmol/L
Alkaline Phosphatase	F	> 832 U/L	> 832 U/L
Alkaline Phosphatase	M	> 1032 U/L	> 1032 U/L
Hematology variables			
Neutrophils	Both	< 1.5 x 10  /µL	< 1.5 x 10  /L

## 2.8.4 Other safety data

### 2.8.4.1 ECG and cardiac imaging data

For the numeric ECG measurements

- ECG Mean Heart Rate
- PR Interval
- QRS Duration
- QT Interval
- QTcF Interval
- RR Interval

summary statistics will be presented for baseline and week 24 separately for each treatment group. Descriptive summary statistics for the change from baseline to the week 24 will be calculated for patients with available ECG data at both time points.

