3.6 Risks and benefits

Erenumab is being developed for migraine prophylaxis in a large clinical development program including more than 3.000 patients and has shown efficacy across the migraine spectrum. Key risks and benefits are briefly summarized below. For further information, please refer to the most recent Investigator Brochure.

There were no significant findings in the toxicology studies with erenumab that would predict a risk to human patients. There were no significant effects on electrocardiogram (ECG) parameters, blood pressure or respiration rate in the single dose cardiovascular study in cynomolgus monkeys.

Safety results from studies (studies 20120178, 20120295, 20120296 and 20120297, and CAMG334A2301) indicate that the frequency of treatment-emergent adverse events (AEs) and discontinuations due to AE were similar between erenumab and placebo. Overall, there was no apparent dose-dependency in the incidence of AEs. Most treatment-emergent adverse events were grade 1 or 2 based on the Common Terminology Criteria for Adverse Events (CTCAE). Most commonly reported AEs ($\geq 3\%$ in any group) included nasopharyngitis, fatigue, headache, back pain and influenza. There were no clinically significant changes in laboratory values, vital signs and electrocardiograms.

As of 31 January 2018 an estimated 4298 subjects (3576.67 subject-years) have been exposed to erenumab in clinical trials conducted by Amgen and Novartis since the beginning of the development program. The integrated safety data set comprised 2537 subjects with migraine, representing 2310.3 SY of exposure.

A theoretical cardiovascular safety risk with CGRP receptor blockade is lack of compensatory vasodilation, particularly in the context of the coronary circulation during ischemic-related conditions. Overall, to date, there is no evidence from nonclinical and clinical data of risk of cardiovascular effects. However, based on the theoretical basis of the mechanism of action of erenumab, cardiovascular effects continue to be monitored in clinical trials.

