5.6.2 Discontinuation of study treatment

Discontinuation of study treatment for a patient occurs when study drug is stopped earlier than the protocol planned duration, and can be initiated by either the patient or the investigator.

The investigator must discontinue study treatment for a given patient if, on balance, he/she believes that continuation would negatively impact the risk/benefit of trial participation.

Study treatment must be discontinued under the following circumstances:

- Patient wish
- Pregnancy (see Section 6.5.6 and Section 7.5)
- Use of prohibited treatment as per recommendations in Table 5-1
- Any situation in which study treatment might result in a safety risk to the patient
- Any laboratory abnormalities that in the judgment of the investigator, taking into consideration the patient's overall status, prevents the patient from continuing participation in the study

If discontinuation of study treatment occurs, the patient should NOT be considered withdrawn from the study, and should continue recording in the eDiary as per protocol. Also, patients who discontinued treatment from the double-blind treatment epoch will follow the abbreviated visit schedule until the follow up visit (week 28) is reached (Table 6-2). These visits should be performed with all assessments outlined in Table 6-2. At a minimum, the following data should be collected at clinic visits or via telephone visits:

- new/concomitant treatments
- adverse events / serious adverse events

If the patient cannot or is unwilling to attend any visit(s), the site staff should maintain regular telephone contact with the patient, or with a person pre-designated by the patient. This telephone contact should preferably be done according to the study visit schedule.

Patients who prematurely discontinue the study for any reason should be scheduled for a visit as soon as possible, at which time all of the assessments listed for the final visit (Visit 199) will be performed. At this final visit, the adverse event and concomitant medications should be reconciled on the eCRF. Patients will return for a follow-up visit approximately 8 weeks after their last dose of study medication, and perform the study procedures outlined in Table 6-1.

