**2.1.1.2 Visit and analysis window**

Since the actual visit for a subject may not exactly coincide with their targeted visit date, the actual visit date is mapped to a study visit.

The nearest study day window will be utilized to define study visit for lab, vital signs, ECG, C-SSRS and some PROs collected during office visits (HIT-6, SF-36v2, ██████████) before dose is administered.

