### 2.1.1.5 Safety Endpoints

Analyses on Adverse Events will be performed for the entire study without differentiating between the DBTE and Follow-up epoch. Independently, whether a patient is an ASA-patient or not, AEs will be analysed in the following analysis window:

[Study Day 1; EoS Date]

Remaining safety analyses will be performed for the DBTE and Follow-up Epoch separately. Laboratory, vital signs, ECG and C-SSRS are assessed during study visits and, therefore, will be assigned to the DBTE based on (Table 2.1.1.2-1).

Concomitant medications will be assigned to the DBTE based on the following analysis window:

[Study Day 1; Week 24 visit date if the visit was performed / MIN(EoS, study day 169) if the visit was not performed]

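### A final-visit ECG taken before Day 155 in a patient who leaves the study early is mapped to a visit before Week 24, so its numeric values enter no ECG summary in the SAP

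*SAP*

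**What the plan says.** **Reporting.** SAP 2.8.4.1 lists heart rate and the PR, QRS, QT, QTcF and RR measurements and says that "summary statistics will be presented for baseline and week 24 separately for each treatment group". It adds: "Descriptive summary statistics for the change from baseline to the week 24 will be calculated for patients with available ECG data at both time points".

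**Visit assignment.** SAP 2.1.1.2 says: "The nearest study day window will be utilized to define study visit for lab, vital signs, ECG". Table 2.1.1.2-1 gives Week 24 a target of Day 169 and a window of Days 155 to 182. SAP 2.1.1.5 uses the same table to place ECGs in the double-blind epoch.

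**Patients who leave the study early.** Protocol 5.6.2 calls for a visit as soon as possible, "at which time all of the assessments listed for the final visit (Visit 199) will be performed".

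**Patients who stop treatment but stay in the study.** The same section says that they "will follow the abbreviated visit schedule until the follow up visit (week 28) is reached". Table 6-2 schedules their ECG at V199-ASA, which is Week 24.

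**Why ECGs matter here.** Protocol 3.6 describes a theoretical cardiovascular risk from blocking the CGRP receptor and says that "cardiovascular effects continue to be monitored in clinical trials".

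**The concern.** Each rule is reasonable alone, but together they leave a gap. A final visit brought forward because the patient is leaving keeps its real study day. Its ECG is then filed under whichever visit is nearest, and SAP 2.8.4.1 reports none of the visits between baseline and Week 24.

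The resulting table describes patients seen at about six months, but nothing in SAP 2.8.4.1 labels it that way. Some leavers go for safety reasons. For example, Protocol 5.5.9 requires a patient whose treatment code is broken in an emergency to leave the study. What would be lost is the set of measured values, including shifts in QTcF, PR, QRS or heart rate that no investigator judged clinically significant. At stake is the completeness of one descriptive safety table.

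**Working it through.** **Step 1: reproduce the Week 24 window.** The inputs are the target days in SAP Table 2.1.1.2-1. Under a nearest-day rule, a window starts at the midpoint between adjacent targets.

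- Week 20: (113 + 141) / 2 = 127. The table prints 127.
- Week 24: (141 + 169) / 2 = 155. The table prints 155.

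The other lower bounds from Week 2 onward also match, rounding up where the midpoint is fractional. Day 155 is therefore the true cut-off.

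**Step 2: map example final-visit ECGs.**

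| Day of ECG | Window | Assigned visit | In the ECG summary? |
|---|---|---|---|
| 30 | 26–32 | Week 4 | No |
| 60 | 50–70 | Week 8 | No |
| 120 | 99–126 | Week 16 | No |
| 154 | 127–154 | Week 20 | No |
| 155 | 155–182 | Week 24 | Yes |

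**Step 3: look for another route for the values.** The public SAP text has no early-termination visit, no last-observation or worst-value ECG row, no table of notable QTcF values and no ECG listing. SAP 2.8 rules out imputing missing safety data.

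**Step 4: compare other data that can be collected at the same visit.**

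| Data | SAP section | Reported at | Early final-visit value appears? |
|---|---|---|---|
| Laboratory | 2.8.3 | Each visit; notable values listed | Yes |
| Vital signs | 2.8.4.2 | Each study visit | Yes |
| C-SSRS | 2.8.4.3 | Each visit, plus a maximum-severity shift table | Yes |
| ECG | 2.8.4.1 | Baseline and Week 24 | No |

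**Step 5: size.** The documents give no rate of study drop-out. SAP 1.1 plans about 375 patients per arm. Assume that 5% to 15% leave before Day 155:

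- 375 × 0.05 = 18.75, about 19 per arm.
- 375 × 0.15 = 56.25, about 56 per arm.

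This counts one ECG for every leaver. Some will have no final visit, and some will be seen on or after Day 155, so 19 to 56 is an upper bound under the assumption.

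**Step 6: timing relative to dose.** A patient who stops treatment but stays in the study has the Week 24 ECG whenever treatment ended. If the last injection was on Day 29 and the ECG is on Day 169, the gap is 169 − 29 = 140 days. The Week 24 summary can therefore contain ECGs taken long after the last dose while omitting ECGs taken nearer to stopping in patients who left.

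**The case against.** The strongest reply is that the group is small and its important findings have another route.

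- **Stopping treatment is not leaving the study.** Protocol 5.6.2 keeps treatment stoppers in the study, and Protocol 5.5.4 says the same of patients who cannot tolerate topiramate. Their ECG at V199-ASA normally falls within Days 155 to 182 and is summarised. This stands, and it removes most patients who stop because of an adverse event.
- **Some leavers have no ECG to lose.** Under Protocol 5.6.3, patients who withdraw consent want no further visits, and a final evaluation is only sought. Under Protocol 5.6.4, a patient counts as lost to follow-up only after the scheduled end-of-study visit has passed. This stands.
- **Clinically significant abnormalities are still captured.** Protocol 6.5.5 sends them to the medical history or adverse event pages. SAP 2.1.1.5 analyses adverse events to the end of the study, and SAP 2.8.1 tabulates and lists them. This stands, so the loss is confined to the numeric values.
- **The cardiovascular rationale is indirect.** The risk in Protocol 3.6 concerns compensatory vasodilation during ischaemia, which would show mainly as clinical events, and the same section reports no clinically significant ECG changes in earlier studies. This lowers the priority but does not close the gap.
- **Parts of the plan cannot be seen.** The ECG row of Table 6-1 is not legible, so an ECG at Visit 199 is inferred from Table 6-2 and SAP 2.8.4.1. The output shells mentioned in SAP 2.1 are not public, and some SAP text is redacted. A listing or an extra row there cannot be excluded.

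A reader might infer that every patient leaving before Day 155 loses an ECG, or that the omission differs by arm. The documents support neither. The date of the ECG decides, not the date of leaving. Protocol 3.2 motivates the trial by differences in discontinuing treatment because of adverse events; nothing predicts a difference in leaving the study. Such a difference is plausible but not documented.

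**Conclusion.** The gap is real but narrow. It affects patients who leave the study and attend a final visit before Day 155, and only the measured ECG values from that visit. The window arithmetic reproduces exactly, and no legible passage brings those values into a summary.

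The number affected is unknown. The bound of 19 to 56 per arm rests entirely on the assumed 5% to 15%. The conclusion also assumes that an ECG belongs to Visit 199 and that the unseen output shells do not already cover the point.

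The primary and secondary analyses are untouched. Fixed time-point summaries are a legitimate choice, but the other data in step 4 are reported by visit, so the ECG rule looks like an oversight. Priority is minor.

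**What to change.** In SAP 2.8.4.1, keep the Week 24 summary and add a 'last post-baseline ECG' summary by arm. It should take the early final-visit ECG whatever its study day, show change from baseline, and flag time since last dose so that ECGs near treatment can be told from those long after it.

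The cost is a sentence in the SAP and one extra descriptive table. No new ECGs or visits are needed. If the output shells already contain such a row, a cross-reference in SAP 2.8.4.1 is enough.
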